## **4.2 Exclusion Criteria**

- 4.2.1 Invasive breast cancer. Areas of microinvasion or suspicious for microinvasion on the core biopsy is allowed.
- 4.2.2 History of prior breast cancer treated within the past two years. Patients completing all breast cancer-specific treatment over two years prior to the current diagnosis are eligible.
- 4.2.3 History of prior ductal carcinoma in situ (DCIS) treated within the past two years. Patients completing all treatment for a previous diagnosis of DCIS over two years prior to the current diagnosis are eligible.
- 4.2.4 Prior lobular carcinoma in situ (LCIS) is allowed.
- 4.2.5 Pregnant, unwilling to use adequate contraception during study treatment duration or breastfeeding (see footnote 1 below).
- 4.2.6 Any autoimmune disease or other medical condition that, in the opinion of the investigator, would compromise the subject's safety.
- 4.2.7 Immune deficiency diseases such as immunoglobulin deficiency or immunosuppressive therapy that might interfere with appropriate immune response.
- 4.2.8 Known history of or known active infection with human immunodeficiency virus (HIV), hepatitis B or hepatitis C.

- 4.2.9 Patients on chronic steroid therapy or other immunosuppressive therapy except for topical or inhaled steroids known to have low systemic absorption.
- 4.2.10 Patients with a known hypersensitivity to GM-CSF, yeast-derived products, or any component of the GM-CSF product (*e.g.*, mannitol).
- 4.2.11 Concurrent treatment with other investigational agent.
- 4.2.12 History of non-breast malignancy within 5 years prior to randomization, except curatively treated superficial bladder cancer, carcinoma in situ of the cervix (Stage 0 – 1), and basal cell or squamous cell carcinoma of the skin.
- 4.2.13 History of allergic reactions attributed to compounds of similar chemical or biologic composition to NeuVax.
- 4.2.14. Uncontrolled intercurrent illness including, but not limited to, ongoing or active infection, symptomatic congestive heart failure, unstable angina pectoris, cardiac arrhythmia, or psychiatric illness/social situations that would limit compliance with study requirements.
- 4.2.15. No recent or planned immunotherapy.

 The effects of NeuVax on the developing human fetus are unknown. For this reason and because NeuVax may be teratogenic, pregnant women will be excluded. All heterosexually active women who may become pregnant must agree to use adequate contraception (hormonal or barrier method of birth control; abstinence) prior to study entry and for the duration of study participation OR be post-menopausal defined as any one of the following 1) prior hysterectomy, 2) absence of menstrual period for 1 year in the absence of prior chemotherapy or 3) absence of menstrual period for 2 years in women with a prior history of chemotherapy exposure who were pre-menopausal prior to chemotherapy. Should a woman become pregnant or suspect she is pregnant while participating in this study, she should inform her study physician immediately.

### **4.3 Inclusion of Women and Minorities**

Participants will be adult women of all races and ethnic groups who are at least 18 years old. Breast cancer is extremely rare in men and men have limited amounts of normal breast tissue; therefore, male participants will not be recruited to this trial. Children will not be recruited to the trial because breast cancer is not relevant to the child population.

Our goal is to ensure that the study is available to women of all races and ethnic groups. To ensure enrollment of minorities we will work with the minority community and social network groups available at each accruing site within the US, such as Black Women's Health Imperative, Sisters Network, Army of Women, Cancer Forward, Breast Health Collaborative, Asian Cancer Council (Indian American Cancer Network, Filipino Cancer Network, Light and Salt) and Susan G. Komen Breast Cancer Foundation.

Although minority groups will be targeted in recruitment, the HLA-A2 haplotype is less common in minorities than in Caucasians. In our previous studies close to 77% of HLA-A2 positive participants were Caucasian. This gives us grounds to expect that although we will approach all racial groups, the majority of participants who will test HLA-A2 positive during eligibility verification will be Caucasian.

#### 4.4 Recruitment and Retention Plan

Participants will be recruited for enrollment on this trial from the primary clinics of the Investigators and/or surgical collaborators. Efforts will be made to enroll women from a diversity of ethnic and socio-economic backgrounds. There will be no payments made to participants or physicians for participation in this study. Prior to enrollment on the study, the physician will discuss the study protocol in detail with the patient, including possible toxicities. The informed consent document will be reviewed by the physician with the patient. To facilitate accrual, information about the trial will be advertised, for example, on the websites of participating institutions.

Please refer to the study-specific Recruitment and Retention Plan for more details.

### 5. AGENT ADMINISTRATION

Vaccine and GM-CSF alone inoculations will be administered in the clinic.

#### 5.1 Dose Regimen and Dose Groups: Vaccine dosage and preparation

- *Agents:* The NeuVax vaccine (nelipepimut-S; as 1.5 mg/mL nelipepimut-S acetate solution) will be supplied to the NCI Repository by SELLAS. GM-CSF (as 250 µg lyophilized Leukine) will be supplied by the NCI Repository.
- *Administration:* Using aseptic technique, 0.8 mL of nelipepimut-S acetate solution (1136 µg nelipepimut-S peptide) is added to the re-constituted Leukine. Taking into account vial losses, this procedure will yield a total dose of approximately 1010 µg of nelipepimut-S peptide in a volume of 1.6 mL. Divide 1.6 mL into 4 equally divided 0.4 mL syringes for intradermal injection. The detailed guidance for mixing nelipepimut-S peptide mixed with lyophilized Leukine® (sargramostim, GM-CSF) or Control (sterile water for injection) with Leukine is presented in **Appendix B**.
- *Duration:* Participants randomized to the nelipepimut-S/GM-CSF arm will receive two vaccinations of nelipepimut-S (1000 µg) and GM-CSF (250 µg) administered **intradermally** two weeks apart prior to surgery. Participants randomized to the GM-CSF alone arm will receive inoculations of GM-CSF (250 µg) administered in an identical manner to those receiving nelipepimut-S+GM-CSF.

#### 5.2 NeuVax Inoculation Series Administration

Subjects will receive 2 vaccinations each consisting of 4 intradermal inoculations on the anterior or medial side of the same thigh. The general area of inoculation will be at a location midway between the inguinal ligament and the knee.

The 1.6 mL by volume vaccine (or GM-CSF alone) will be administered **intradermally** in four equal inoculums at four different sites in a square configuration 5 cm from each other. Inoculations will be administered in the same lymph node draining area (same leg). Vaccinations will be made in the same thigh each time (Vaccines #1 through 2 ) to optimize the immune response by using the same draining lymph node each time.

Participants randomized to the nelipepimut-S/GM-CSF arm will receive two vaccinations of nelipepimut-S (1000 µg) and GM-CSF (250 µg) administered intradermally two weeks apart prior to surgery. Participants randomized to the GM-CSF alone arm will receive inoculations of GM-CSF (250 µg) administered in an identical manner to those receiving nelipepimut-S/GM-CSF.

A healthcare provider approved at each institution to deliver inoculations will administer the inoculations sterilely in the clinical facility at each study site. Post inoculation vital signs will be assessed at 30 +/- 5 minutes after inoculation by the research nurse / or coordinator. For female participants with childbearing potential, a urine pregnancy test will be performed before each inoculation. If this test is positive at any time, the participants will be discontinued from the study.

### **5.3 Run-in Procedures**

This trial will not include a run-in period.

### **5.4 Contraindications**

Drug interactions between NeuVax and other agents have not been studied.

Leukine is contraindicated:

1. in patients with excessive leukemic myeloid blasts in the bone marrow or peripheral blood ( $\geq$  10%);
2. in patients with known hypersensitivity to GM-CSF, yeast-derived products or any component of the product;
3. for concomitant use with chemotherapy and radiotherapy.

Due to the potential sensitivity of rapidly dividing hematopoietic progenitor cells, Leukine should not be administered simultaneously with cytotoxic chemotherapy or radiotherapy or within 24 hours preceding or following chemotherapy or radiotherapy. In one controlled study, participants with small cell lung cancer received Leukine and concurrent thoracic radiotherapy and chemotherapy or the identical radiotherapy and chemotherapy without Leukine. The participants randomized to Leukine had significantly higher incidence of adverse events, including higher mortality and a higher incidence of grade 3 and 4 infections and grade 3 and 4 thrombocytopenia. Refer to the rhGM-CSF Leukine® [sargramostim] package insert for information on drug interactions with rhGM-CSF Leukine® [sargramostim].

### **5.5 Concomitant Medications**

All medications (prescription and over-the-counter), vitamin and mineral supplements, and/or herbs taken by the participant will be documented on the concomitant medication CRF and will include: 1) start and stop date, dose and route of administration, and indication.

Participants experiencing a local or systemic reaction to vaccination may be advised to take Tylenol. For significant pruritis at the injection site, participants may use an over the counter oral anti-histamine. Steroids are prohibited unless, in the determination of the Investigator, the participant is experiencing systemic hypersensitivity or an allergic reaction.

### **5.6 Dose Modification**

In our previous trials evaluating Nelipepimut-S + GM-CSF, approximately 18% of patients experienced robust local reactions ( $>100\text{mm}$ ) or greater than or equal to grade 3 local or systemic reactions or greater than or equal to grade 2 hypersensitivity reactions [26]. For a description of how local reaction will be

measured, refer to section 7.3.1. To avoid higher grade toxicities, for participants meeting any of these criteria, we will dose-reduce the GM-CSF component of the vaccine as outlined below. Site PIs cannot make the decision to dose-reduce without consulting with [name]. The decision to dose-reduce the GM-CSF will be made by the Protocol Principal Investigator, [name], who will communicate the need for dose-reduction to the individual site PI and site study research nurse / or coordinator who will be generating the orders for the pharmacy for preparation of vaccine. Adverse events that do not respond to either dose modification or clinical management of the reaction will result in taking the participant off agent but followed for study endpoints (refer to Section 8.3: Off-Agent Criteria).

Inoculations will be immediately halted if any serious adverse reactions occur to include: death, life-threatening adverse drug experience (i.e., severe anaphylactic reaction immediately after vaccine administration), inpatient hospitalization or prolongation of existing hospitalization, a persistent or significant disability/incapacity, a congenital anomaly/birth defect, or other important medical events that may not result in death, be life-threatening, or require hospitalization but which, when based upon appropriate judgment of the PI, be determined to jeopardize the participant or require medical or surgical intervention to prevent an outcome listed above.

Participants experiencing Grade 4 toxicities of any attribution will be taken off agent and followed (refer to Section 8.3: Off-Agent Criteria). Any participant with Grade 3 systemic toxicities possibly, probably or definitely attributable to study drug will be taken off agent and followed, except for participants with skin toxicities. Any participant experiencing Grade 3 skin toxicities will continue to receive inoculations as long as their skin toxicity has resolved prior to the next scheduled inoculation. Participants with Grade 3 toxicities not related or unlikely related to study agent will continue on study.

Dose Reductions of Vaccine. Toxicities observed with the vaccine are attributable to the GM-CSF. Although the toxicity profile of GM-CSF is the same for a 250 µg dose as for a 125 µg dose, the extent of the toxicity will vary between participants. Therefore, the provision for dose reductions of the GM-CSF component of the vaccine is a safety issue for an individual participant. For participants experiencing robust local reactions (>100mm x 100mm); grade 3 local reactions; or greater than or equal to grade 2 hypersensitivity reactions the dose of GM-CSF will be reduced for the subsequent inoculation as outlined in Table 1 below. This dose reduction will be done to decrease the likelihood that the participant will experience the same degree of reaction. Management of hypersensitivity reactions will be at the discretion of the Investigator or an appropriately qualified member of the study team designated by the Investigator.

Dose Reduction of GM-CSF.

*Table 1. Dose Reduction Using Reconstituted Lyophilized Leukine*

	Amount of reconstituted Leukine® solution removed prior to addition of E75 acetate solution	Amount of WFI diluent added back to E75 acetate solution	Dose of rhGM-CSF
No dose reduction	0 mL	0 mL	250 µg
1 st dose reduction	0.5 mL	0.5 mL	125 µg

In our prior trial, approximately 5% of patients developed delayed urticarial reactions (generalized urticaria 10-14 days after booster inoculation). This was not seen during the primary vaccination series.

The majority of these patients were readily treated with anti-histamines or oral steroids and most continued with subsequent booster inoculations. If dose reduction is performed for hypersensitivity reactions (generalized urticaria), over the counter antihistamines may be used before or after subsequent inoculations at the discretion of the Investigator or an appropriately qualified member of the study team designated by the Investigator. If urticaria persists with the use of over the counter anti-histamines, then prescription anti-histamines will be prescribed. If urticarial persists with the use of prescription anti-histamines, the participant will be give oral steroids (Medrol Dosepak). If the urticarial continues to persist then the participant will be given intravenous steroids. Use of intravenous steroids has been required in <1% of participants on prior trials evaluating this vaccine. If intravenous steroids or hospitalization are required, or in the opinion of the Principal Investigator, further inoculations will be discontinued, the participant will be taken off agent but followed for study endpoints (refer to Section 8.3: Off-Agent Criteria).

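### Section 5.6 does not say whether stopping or GM-CSF dose reduction governs a rare non-serious grade 3 non-skin reaction after injection 1, and Section 6.9.5 ends follow-up after unblinding for an SAE (minor)

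*Combined protocol and SAP*

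**What the plan says.** Section 5.6 deals with reactions in several places.

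- **Opening paragraph.** It lists reactions seen in earlier trials: large local reactions, local or systemic reactions of grade 3 or higher, and hypersensitivity of grade 2 or higher. It then says "for participants meeting any of these criteria, we will dose-reduce the GM-CSF component of the vaccine as outlined below". The decision is central: "The decision to dose-reduce the GM-CSF will be made by the Protocol Principal Investigator".
- **Second paragraph.** "Inoculations will be immediately halted if any serious adverse reactions occur". Its list of serious reactions ends with other medically important events, as judged by the PI.
- **Third paragraph.** Grade 4 toxicity of any attribution means off agent. For grade 3: "Any participant with Grade 3 systemic toxicities possibly, probably or definitely attributable to study drug will be taken off agent and followed". Skin reactions are the only exemption: at grade 3 they may continue once resolved.
- **Dose Reductions of Vaccine.** For "greater than or equal to grade 2 hypersensitivity reactions the dose of GM-CSF will be reduced for the subsequent inoculation". No upper grade is given. This list also has large and grade 3 local reactions but, unlike the opening paragraph, no systemic reactions. The same paragraph leaves management of hypersensitivity to the Investigator's judgement.
- **Closing text on urticaria.** Hypersensitivity leading to dose reduction is glossed as generalized urticaria. Further: "If intravenous steroids or hospitalization are required, or in the opinion of the Principal Investigator, further inoculations will be discontinued".

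Section 6.9.5 allows unblinding when medically necessary after a serious adverse event (SAE). At step 5 the site PI breaks the blind and removes the participant from the study. Section 8.3 lists an SAE among the off-agent reasons and keeps such participants, where possible, in safety and endpoint follow-up. Section 8.4 includes SAEs among the reasons for which a participant may go off-study.

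**The concern.** Two rules in one section, both worded as what will happen, can apply to the same participant and lead to opposite actions. One gives a second, reduced dose of GM-CSF; the other gives none. No sentence ranks them. Read literally, the dose-reduction text could re-expose someone whom the stop rule withdraws.

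The choice also decides membership of the primary analysis set. Section 5.7 counts a participant as evaluable only if all pre-surgical vaccinations were given. A participant stopped after injection 1 is therefore not evaluable, while one given a reduced dose can be. Investigators know the arm (Section 6.9.2), so a written rule is better than settling each case as it arises.

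The unblinding step raises a separate matter. Breaking the blind is no reason in itself to stop observing a participant. Going off-study gives up the remaining scheduled safety assessments, including the post-vaccination ECHO in Section 7.4.1, and the remaining CTL samples.

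**Working it through.** **1. Which reactions after injection 1 are left open?** Only two injections are given (Section 5.2), so only a reaction to the first can trigger either rule.

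| Reaction | Dose-reduction text | Stop text | Outcome |
|---|---|---|---|
| Grade 2 hypersensitivity, not serious | Reduce | None by grade | Reduce |
| Grade 3 skin reaction | Reduce, if hypersensitivity | Exempt; continue once resolved | Continue, reduced |
| Serious, including medically important | Reduce, if hypersensitivity | Immediate halt | Halt |
| Needs intravenous steroids or hospitalization | Reduce, if hypersensitivity | Discontinue | Stop |
| Grade 4 | Reduce, if hypersensitivity | Off agent; also life-threatening by the Section 11.1.3 scale, so halted as serious | Stop |
| Grade 3, non-skin, attributable, not serious | Reduce | Off agent | **Not settled** |

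The last row is narrow. The grade 3 description in Section 11.1.3 includes hospitalization being indicated, so many such reactions would be serious.

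**2. How often might it occur?** Section 6.2 reports one grade 3 angioedema in the early trials. The two phase III hypersensitivity cases were grade 2 and grade 4, and no other allergic reactions are reported. The numerator is 1. The denominator is an assumption:

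- 108: vaccinated phase I/II participants (Section 2.3)
- 187: all phase I/II participants, controls included
- 108 + 758/2 = 487: adding half of phase III, assuming 1:1 allocation
- 108 + 758 = 866: adding all of phase III

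With rate p, the expected number in 48 is 48p, and the chance of at least one is 1 − (1 − p)^48.

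| p | 48p | Chance of at least one |
|---|---|---|
| 1/866 | 0.06 | 5.4% |
| 1/487 | 0.10 | 9.4% |
| 1/187 | 0.26 | 22.7% |
| 1/108 | 0.44 | 36.0% |

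These rates cover whole vaccination series. Section 2.3 places the peak CTL response after the third inoculation, so the earlier series had at least three. The risk after injection 1 alone is lower, but the documents do not split events by injection.

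**3. Effect on power.** Section 13.1 states 82% for 27 v 13 evaluable, effect size 1, two-sided t-test at 0.05. The noncentrality is √(27 × 13/40) = 2.96 on 38 degrees of freedom, and the noncentral t distribution gives 82.3%, so the plan's figure reproduces. Losing one evaluable participant gives 81.8% (26 v 13) or 80.1% (27 v 12).

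**4. Unblinding.** Take a grade 4 SAE that leads to unblinding. Section 5.6 says off agent and followed. Section 8.3 says continue safety and endpoint follow-up. Section 6.9.5 step 5 says off-study. Section 8.4 permits off-study for an SAE but does not require it. After that, what remains is an early termination visit when possible (8.4) and follow-up of agent-related SAEs until resolved (11.2.2.6). The frequency of unblinding for an SAE cannot be estimated from the documents.

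**The case against.** The rules in 5.6 can be read together. Reducing the dose at a subsequent injection presupposes that there is one, and the third paragraph decides who receives it. On that reading the missing upper grade has a purpose: it covers grade 3 skin hypersensitivity, which continues. The urticaria gloss fits this. The opening paragraph defers to the list below it, and that list omits systemic reactions. Further text points to stopping: the halt for serious and medically important events, the Section 5.4 contraindication of Leukine in known GM-CSF hypersensitivity, discontinuation on the Principal Investigator's opinion, the Investigator's discretion over managing hypersensitivity, and the central dose-reduction decision. The one earlier case, listed in Section 6.2 as angioedema of the tongue, might well have been halted as medically important.

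Most of this stands, and it makes re-exposure unlikely. It does not state precedence. Naming who decides is not the same as saying which rule governs.

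On unblinding, Section 8.4 does list SAEs, so 6.9.5 has support elsewhere in the protocol, and follow-up under 8.3 is itself only where possible. That also stands. But 8.4 is permissive whereas 6.9.5 is automatic, and nothing explains why breaking the blind should end follow-up.

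**Conclusion.** The point holds as two minor wording faults. Section 5.6 leaves one rare case under two rules with no stated precedence. Section 6.9.5 makes off-study automatic where 5.6 and 8.3 intend follow-up. The frequency of the first cannot be estimated reliably from a single event: 5% to 36% for at least one case in 48 spans the assumed denominators, and the figure for injection 1 alone is lower. Planned power is unaffected.

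Three stronger readings are not supported.

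- A reader might infer that every grade 3 systemic reaction is caught. At the 2% earlier rate, that would be about one participant (48 × 0.02 = 0.96). But the opening paragraph points to a list that omits systemic reactions, and the 2% combines bone pain with angioedema over a longer series.
- A reader might infer that the protocol directs sites to re-expose patients after severe allergy. The surrounding text favours stopping, and sites cannot reduce the dose on their own.
- A reader might infer that the unblinding rule threatens the primary analysis. Keeping the participant on study restores primary-endpoint evaluability only if both injections had already been given. Otherwise it recovers safety data, secondary data and the comparison with non-evaluable participants that Section 13.8 plans.

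**What to change.** In Section 5.6:

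- Add a sentence: *Where a stop rule and a dose-reduction rule both apply, the stop rule takes precedence.*
- Under Dose Reductions of Vaccine, limit the hypersensitivity trigger to grade 2 reactions and to grade 3 skin-only reactions that have resolved before the next inoculation.
- In the opening paragraph, refer to the criteria listed under Dose Reductions of Vaccine instead of to the reactions seen in earlier trials. The cited description of those trials can stay.

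In Section 6.9.5 step 5, replace off-study with: *off agent, with safety and endpoint follow-up continued under Section 8.3 unless the participant withdraws*.

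The cost is a wording amendment and a notice to sites. No procedures are added beyond the existing schedule of events, and no participants.
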